8.2 Standard of Care Agents Dose Modifications (not lenalidomide)

8.21 Standard of care dose modifications will be adjusted as per standard of care guidelines in the prescribing information for multiple myeloma patients.

8.3 Dexamethasone–Related Treatment Modification Guidelines for Adverse Events

8.31 Dexamethasone Dose Modifications

Dose Level	Dexamethasone (Cycle 1: Day 1, 8, 15) Cycle 2-6: Day 1, 8, 15, 22 (Age <75)	Dexamethasone (Cycle 1: Day 1, 8, 15) Cycle 2-6: Day 1, 8, 15, 22 (Age ≥75)
Starting Dose	40 mg	20 mg
-1	20 mg	8 mg
-2	8 mg	Discontinue
-3	Discontinue	

→ → Use the NCI Common Terminology Criteria for Adverse Events (CTCAE) version 5.0*
unless otherwise specified ← ←

CTCAE SOC	Adverse event	Severity	Action on Dexamethasone
Gastrointestinal disorders	Dyspepsia, ulcer, or gastritis	Grade 1-2	Treat with histamine-H2 receptor blockers, sucralfate, or proton-pump inhibitors. If symptoms persist despite these measures, decrease by 1 dose level.
		≥Grade 3	Omit dexamethasone until symptoms adequately controlled. Restart and decrease 1 dose level of current dose along with concurrent therapy with histamine-H2 receptor blockers, sucralfate, or omeprazole. If symptoms persist despite these measures, discontinue and do not resume
	Pancreatitis	≥Grade 3	Permanently discontinue
General disorders and administration site conditions	Localized edema	≥Grade 2	Intervention indicated (eg, diuretics) as needed and decrease by 1 dose level. If edema persists despite these measures, decrease dose another level at investigator discretion. Discontinue and do not resume if symptoms persist despite 2nd reduction.
Psychiatric disorders	Confusion or Agitation	≥Grade 2	Omit dexamethasone until symptoms resolve. Restart with 1 dose level reduction. If symptoms persist despite these measures, permanently discontinue dexamethasone.
Musculoskeletal and connective tissue disorders	Generalized muscle weakness	≥Grade 2	Decrease dexamethasone dose by 1 dose level. If weakness persists despite these measures, decrease dose further by 1 dose level at investigator discretion. Permanently discontinue dexamethasone if symptoms persist.

CTCAE SOC	Adverse event	Severity	Action on Dexamethasone
Metabolism and nutrition disorders	Hyperglycemia	≥Grade 2	Treatment with insulin or oral hypoglycemia as needed. If uncontrolled despite these measures, decrease dose by 1 dose level until blood glucose levels are satisfactory

Located at http://ctep.cancer.gov/protocolDevelopment/electronic_applications.ctc.htm

** Use the following to describe actions in the Action column:

- **Omit** = The current dose(s) for the specified drug(s) during a cycle is skipped. The patient does not make up the omitted dose(s) at a later time
- **Hold/Delay** = The current dose(s) of all drugs during a cycle is delayed. The patient does make up the delayed dose(s) when the patient meets the protocol criteria to restart drugs.
- **Discontinue** = The specified drug(s) are totally stopped.

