17.0 Pathology Considerations/Tissue Biospecimens NA.....	58
18.0 Records and Data Collection Procedures.....	58
19.0 Budget.....	59
20.0 References.....	60
Appendix I ECOG Performance Status.....	62

Schema

*Sample collection under IRB#14-009163, IRB#919-04, or IRB#521-93

**Dosing and regimen as per section 7

***Patients who discontinue treatment before completing 6 cycles for any reason will go off study (No SFU/CFU).

[†]Cycle 1 = 21. Cycles 2 – 6 = 28 days

Generic name: Lenalidomide	Generic name: Pomalidomide	Generic name: Dexamethasone
Brand name(s): Revlimid	Brand name(s): Pomalyst	Brand name(s):
Mayo Abbreviation:	Mayo Abbreviation:	Mayo Abbreviation:
Availability: Commercial	Availability: Commercial	Availability: Commercial

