3.0 Registration Patient Eligibility

3.1 Registration - Inclusion Criteria

3.11 Age \geq 18 years

3.12 **Cohort A:** Patient must have untreated smoldering multiple myeloma which is defined by the presence of 10% or more but less than 60% clonal plasma cells in the bone marrow and the absence of any of the following myeloma related symptoms or laboratory and radiographic abnormalities: anemia, hypercalcemia, renal insufficiency, hypercalcemia, serum free light chain ratio of greater than 100 or more than one focal marrow multiple myeloma lesion on MRI imaging.

Cohort B: Patient must have newly diagnosed myeloma requiring treatment and no prior therapies

Cohort C: Patient must have relapsed or refractory multiple myeloma with at least one prior therapy for their multiple myeloma but not refractory to all IMiDs

Cohort D: Patient must have relapsed or refractory multiple myeloma with Lenalidomide as part of a maintenance regimen as their most recent therapy

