7.0 Protocol Treatment

7.1 Treatment Schedule

Cohort A and B Cycle 1

Treatment medication table. Patient may receive Lenalidomide OR Lenalidomide + Dexamethasone.

Agent	Dose Level	Route	Day	Re Rx
Lenalidomide	25 mg*	Oral	Cycle 1: Day 1-14	Cycle 1: 21 days
Dexamethasone	40 mg**	Oral	Cycle 1: Day 1 ,8, ,15	Cycle 1: 21 days

Cycle 1 length = 21 days

* Starting dose will be determined as per the creatine clearance below (see 7.12)

**The dose of dexamethasone used can be determined by the treating physician and omitted if needed.

Cohort C and D Cycle 1

Treatment medication table. Patient may receive Lenalidomide + Dexamethasone OR Pomalidomide + Dexamethasone.

Agent	Dose Level	Route	Day	ReRx
Lenalidomide	25 mg*	Oral	Cycle 1: Day 1-14	Cycle 1: 21 days
Pomalidomide	4 mg	Oral	Cycle 1: Day 1-21	Cycle 1: 21 days
Dexamethasone	40 mg**	Oral	Cycle 1: Day 1 ,8, ,15	Cycle 1: 21 days

Cycle 1 length = 21 days

* Starting dose will be determined as per the creatinine clearance below (see 7.12)

** The dose of dexamethasone used can be determined by the treating physician and omitted if needed.

Cohort A and B Cycles 2-6

Treatment Medication Table. Patient may receive Lenalidomide based regimens.

Agent	Dose Level	Route	Day	Re Rx
Lenalidomide	25 mg*	Oral	Cycle 2-6: Day 1-21	Cycles 2-6: 28 days
Dexamethasone	40 mg**	Oral	Cycle 2-6: Day 1 ,8, ,15, 22	Cycles 2-6: 28 days

Note: Standard of care agents can be added for cycles 2-6 as long as the regimen contains lenalidomide

Cycles 2-6 length = 28 days

* Any dose-adjustments will be determined as per the creatine clearance below (see 7.12).

** The dose of dexamethasone used can be determined by the treating physician and omitted if needed.

Cohort C and D Cycles 2-6

Treatment medication table. Patient may receive Lenalidomide based regimen OR Pomalidomide based regimen.

Agent	Dose Level	Route	Day	ReRx
Lenalidomide	25 mg*	Oral	Cycles 2-6: Day 1-21	Cycles 2-6: 28 days
Pomalidomide	4 mg	Oral	Cycles 2-6: Day 1-21	Cycles 2-6: 28 days
Dexamethasone	40 mg**	Oral	Cycle 2-6: Day 1,8,15,22	Cycles 2-6: 28 days

Note: Standard of care agents can be added for cycles 2-6 as long as the regimen contains lenalidomide or pomalidomide

Cycles 2-6 length = 28 days

* Any dose-adjustments will be determined as per the creatinine clearance below (see 7.12).

** The dose of dexamethasone used can be determined by the treating physician and omitted if needed.

7.12

Creatinine Clearance (CrCl)	Lenalidomide Dose

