8.0 Dosage Modification Based on Adverse Events

Any adverse event noted in the study and its resultant dose-modifications should be managed as per the prescribing information of lenalidomide, dexamethasone and/or pomalidomide as per which of these two drugs the adverse event is attributable to.

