15.3 Dexamethasone for Oral Administration (DXM)

15.31 **Background:** Dexamethasone is an adrenal corticosteroid compound. Dexamethasone decreases inflammation by suppression of neutrophil migration, decreased production of inflammatory mediators, and reversal of increased capillary permeability; suppresses normal immune response. Dexamethasone's mechanism of antiemetic activity is unknown.

15.32 **Formulation:** Commercially available for oral administration as:
Tablets [scored]: 0.5 mg, 0.75 mg, 1 mg, 1.5 mg, 2 mg, 4 mg, and 6 mg
Solution, oral: 0.5 mg/5 mL (500 mL)
Solution, oral concentrate: Dexamethasone Intensol: 1 mg/mL (30 mL)

15.33 **Preparation, storage, and stability:** Refer to package insert for complete preparation and dispensing instructions. Store oral tablets at room temperature between 20°C to 25°C (60°F to 77°F). Protect from moisture. Dispense in a well-closed, light-resistant container as defined in the USP/NF. Store oral liquid at room temperature, do not freeze. Do not use if solution contains a precipitate. Refer to commercial package for drug expiration date.

15.34 **Administration:** Refer to the treatment section for specific administration instructions. May be taken with meals to decrease GI upset.

15.35 **Pharmacokinetic information:**
Onset of action: Prompt
Duration of metabolic effect: 72 hours
Metabolism: Hepatic
Half-life elimination: Normal renal function: 4 ± 0.9 hours; **Biological half-life:** 36-54 hours
Time to peak, serum: Oral: 1-2 hours
Excretion: Urine (~10%)

15.36 **Potential Drug Interactions:**
Cytochrome P450 Effect: Substrate of CYP3A4 (major), P-glycoprotein/ABCB1; **Induces** CYP2A6 (weak/moderate), 2C9 (weak/moderate), 3A4 (weak), UGT1A1
Increased Effect/Toxicity: Aprepitant, azole antifungals, calcium channel blockers, cyclosporine, estrogens, and macrolides may increase the serum levels of corticosteroids. Corticosteroids may increase the hypokalemic effects of amphotericin B or potassium-wasting diuretics (loop or thiazide); monitor. Refer to the package insert for a listing of other drugs.
Decreased Effect: Antacids and bile acid sequestrants may reduce the absorption of corticosteroids, separate administration by 2 hours. Aminoglutethimide, barbiturates, and CYP3A4 inducers may reduce the serum levels/effects of dexamethasone. Serum concentrations of isoniazid

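### The section 7.1 treatment tables print dexamethasone 40 mg at any age, while table 8.31 starts patients aged 75 or over at 20 mg

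*Combined protocol and SAP*

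**What the plan says.** Section 7.1 has four treatment tables: Cohorts A and B in cycle 1, Cohorts C and D in cycle 1, and the same two pairs in cycles 2-6. Each has the row "Dexamethasone 40 mg Oral" with a footnote marker on the dose. The footnote, repeated under each table, reads "The dose of dexamethasone used can be determined by the treating physician and omitted if needed". It mentions no age, no 20 mg dose and no other section.

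Section 8.31 sets out dexamethasone dose levels in two age columns. The row for the first level reads "Starting Dose 40 mg 20 mg": 40 mg under 75, and 20 mg in the column headed "Cycle 2-6: Day 1, 8, 15, 22 (Age ≥75"). The older column then steps to 8 mg and to discontinuation. The younger column steps to 20 mg, 8 mg and discontinuation. No other part of the document gives a dexamethasone dose by age.

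Three other places bear on which section a prescriber reads:

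- The schema says "Dosing and regimen as per section 7".
- Section 15.34, on dexamethasone administration, says "Refer to the treatment section for specific administration instructions. May be taken with meals to decrease GI upset".
- Section 8.31 belongs to the section headed "8.0 Dosage Modification Based on Adverse Events".

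The age criterion is "3.11 Age \geq 18 years", with no upper limit.

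**The concern.** For one identifiable group, patients aged 75 or over, the protocol states two different starting doses. The higher one stands where the first order is written. The lower one stands in a section about dose changes after adverse events, and a prescriber has no adverse event to look up before the first dose. Both pointers to dosing instructions (the schema and 15.34) lead to the higher figure.

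Steroid exposure in older patients is at stake. Section 1.0 gives a median age at onset of 65-70 years, and performance status up to ECOG 3 is allowed (3.16), so some patients aged 75 or over are likely to enrol. The documents give no expected number.

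There is a second effect. Section 8.31 orders reductions by one dose level for events such as confusion, muscle weakness or uncontrolled hyperglycemia. A patient aged 75 or over who was started on 40 mg is at a level that does not exist in that patient's column. One level down could then be read as 20 mg or as 8 mg, and the question would arise when the patient already has steroid toxicity.

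**Working it through.** The plan states no figure to reproduce here. The check compares the two sections and then counts doses.

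**Side by side**

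| | Section 7.1 (all four tables) | Section 8.31 |
|---|---|---|
| Age under 75 | 40 mg | 40 mg |
| Age 75 or over | 40 mg | 20 mg |
| Age rule stated | No | Yes |
| Reference to the other section | None to 8.31 | None to 7.1 |
| Discretion | Physician may set or omit the dose | Not mentioned for the starting dose |

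The sections agree for patients under 75. For patients aged 75 or over the printed starts differ by a factor of 40/20 = 2. Giving 20 mg satisfies both sections because of the 7.1 footnote. Giving 40 mg follows the 7.1 table but not the older column of 8.31.

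The same 7.1 tables show how a patient-specific start can be flagged. The lenalidomide dose has a footnote that ties the starting dose to creatinine clearance and refers the reader to 7.12. Dexamethasone has an age-specific start in 8.31 but no such reference.

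**Number of scheduled doses** (days from 7.1 and 8.31)

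- Cycle 1: days 1, 8, 15 = 3 doses.
- Cycles 2-6: days 1, 8, 15, 22 = 4 doses × 5 cycles = 20 doses.
- Total: 3 + 20 = 23 doses.

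**Scheduled dose for a patient aged 75 or over**

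| Assumed course | From 7.1 | From 8.31 | Excess |
|---|---|---|---|
| Corrected after one dose | 40 mg | 20 mg | 20 mg |
| Cycle 1 only | 3 × 40 = 120 mg | 3 × 20 = 60 mg | 60 mg |
| 40 mg in cycle 1, then 20 mg | 120 + 20 × 20 = 520 mg | 23 × 20 = 460 mg | 60 mg (60/460 = 13.0%) |
| 40 mg at all 23 doses | 23 × 40 = 920 mg | 460 mg | 460 mg (two-fold) |

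The first three rows rest on assumed times of correction, which the protocol does not describe. The last row is an upper bound: it needs no dose reduction, no omission and no use of discretion in six cycles.

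**The case against.** The strongest reply is that nothing conflicts. The footnote makes 40 mg a nominal dose, the physician may give 20 mg, and 20 mg complies with both sections. The age rule is in the protocol, in a row labelled as a starting dose, and section 8 also repeats the starting doses of lenalidomide and pomalidomide, so it is a normal place to find them. In Cohorts A and B some patients may take lenalidomide alone in cycle 1 and get no dexamethasone. On this view all that is missing is a cross-reference, and the cumulative-dose figures describe courses that nobody expects.

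Much of this is fair. It is not a hard contradiction, the cumulative figures are illustrative, and the factor of two per dose is the only figure that needs no assumed course. But permission to choose 20 mg does not tell the prescriber that 20 mg is the stated start at this age, and 7.1 read alone gives 40 mg as the default.

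Two further objections concern the remedy. First, the documents do not say which section governs, so the sponsor should confirm that the 8.31 age rule is intended. Second, a starting-dose split in the cycles 2-6 tables might be read as restoring a dose already reduced. That risk exists equally with the 40 mg printed there now. Keeping discretion also means that a physician could still start an older patient at 40 mg, but this would then be a deliberate choice.

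**Conclusion.** The concern holds. Sections 7.1 and 8.31 print different dexamethasone starting doses for patients aged 75 or over, and the section to which prescribers are sent has the higher one with no age rule. The size is 40 against 20 mg per dose and 120 against 60 mg in cycle 1. The 460 mg excess over six cycles is a ceiling and not an expected effect. How many patients this touches is unknown.

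The conclusion rests on the printed text of the two sections and on the assumption that some sites will write the first order from the 7.1 table without consulting 8.31. It does not depend on any overdose having occurred. Patients under 75 are not affected, and neither the sample size nor the way the response rate is estimated changes. The sponsor should correct it because it bears on the safety of older patients and is easy to put right.

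**What to change.** Once the sponsor has confirmed the age rule in 8.31, replace the dexamethasone dose in each of the four 7.1 tables with: *40 mg (age <75) or 20 mg (age ≥75), see 8.31*. Keep the footnote marker and the physician-discretion footnote.

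The sponsor's clinical team may also wish to add a sentence to 8.31 on how to step down when a patient was started at a dose outside their own column. This is optional.

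The cost is one line in four tables. No visit, test or analysis is added, and sample size and timeline stay as they are.

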8.4 Pomalidomide–Related Treatment Modification Guidelines for Adverse Events

8.41 Pomalidomide Dose Modifications

Pomalidomide (Cycle 1: Day 1-21 Cycle 2-6: Day 1-21)	
Dose Level	
Starting dose	4 mg
-1	3 mg
-2	2 mg
-3	1 mg
-4	Discontinue

→ → Use the NCI Common Terminology Criteria for Adverse Events (CTCAE) version 5.0*
unless otherwise specified ← ←

CTCAE System/Organ/Class (SOC)	ADVERSE EVENT	AGENT	ACTION**
Investigations	Neutrophil count decreased If ANC $<1.0 \times 10^9/L$ or ANC $>1.0 \times 10^9/L$ (up to LLN) with fever (temperature $>38.5^{\circ}C$)	Pomalidomide	Omit pomalidomide dose. Follow CBC weekly. If neutropenia has resolved to \leq Grade 2 prior to Day 21 and fever has resolved, restart pomalidomide at next lower dose level and continue through Day 21 of a 28-day cycle. If febrile neutropenia is the only toxicity for which a dose reduction is required, G-CSF may be used and the pomalidomide dose maintained.

CTCAE System/Organ/Class (SOC)	ADVERSE EVENT	AGENT	ACTION**
Investigations	Platelet count decreased If platelet count $<30 \times 10^9/L$	Pomalidomide	Omit pomalidomide dose Follow CBC weekly Hold anticoagulation/antiplatelet therapy until platelets $\geq 50,000/mm^3$ If platelet count resolves to \leq Grade 2 prior to Day 21, restart pomalidomide at next lower dose level and continue through Day 21 of each cycle
Skin and subcutaneous tissue disorders	Rash maculopapular Grade 2 or 3	Pomalidomide	Omit pomalidomide dose; follow weekly If the AE resolves to \leq Grade 1 prior to Day 21, restart pomalidomide at next lower dose level and continue through Day 21 of each cycle
	Grade 3-4 Stevens –Johnson Syndrome	Pomalidomide	Discontinue pomalidomide and remove patient from all study treatment
	\geq Grade 3 Erythema multiforme	Pomalidomide	Discontinue pomalidomide and remove patient from all study treatment
	Erythroderma \leq Grade 3	Pomalidomide	Omit pomalidomide dose; follow weekly If the AE resolves to \leq Grade 1 prior to Day 21, restart pomalidomide at next lower dose level and continue through Day 21 of the 28-day cycle
	Rash, maculo-papular Rash, acneiform Grade 4	Pomalidomide	Discontinue pomalidomide and remove patient from all study treatment
Nervous system disorders	Peripheral sensory neuropathy Grade 3	Pomalidomide	Omit pomalidomide dose and follow at least weekly. If the AE resolves to \leq Grade 1 prior to Day 21, restart pomalidomide at next lower dose level and continue through Day 21
	Peripheral sensory neuropathy Grade 4	Pomalidomide	Discontinue pomalidomide and remove patient from all study treatment

CTCAE System/Organ/Class (SOC)	ADVERSE EVENT	AGENT	ACTION**
Immune system disorders	Allergic reaction Grade 2-3	Pomalidomide	Omit dose and follow at least weekly If the AE resolves to \leq Grade 1 prior to Day 15, restart at next lower dose level and continue through Day 21
	Allergic reaction Grade 4	Pomalidomide	Discontinue pomalidomide and remove patient from all study treatment
Vascular disorders	Thromboembolic event \geq Grade 3	Pomalidomide	Omit dose and start anticoagulation Restart at investigator's discretion (maintain dose level)
Endocrine disorders	Hyperthyroidism or Hypothyroidism \geq Grade 2	Pomalidomide	Omit pomalidomide for remainder of cycle, evaluate etiology, and initiate appropriate therapy Reduce the dose of pomalidomide by 1 dose level.
Other non-hematologic adverse event	Other non-hematologic \geq Grade 3	Pomalidomide	If the AE can be attributed to either of the drugs, pomalidomide should be discontinued at first instance b for recurrence of the same toxicity necessitating dose modification Omit pomalidomide dose. Follow at least weekly If the toxicity resolves to \leq Grade 2 prior to Day 21, restart pomalidomide at next lower dose level and continue through Day 21

* Located at http://ctep.cancer.gov/protocolDevelopment/electronic_applications.ctc.htm

** Use the following to describe actions in the Action column:

- Omit = The current dose(s) for the specified drug(s) during a cycle is skipped. The patient does not make up the omitted dose(s) at a later time
- Hold/Delay = The current dose(s) of all drugs during a cycle is delayed. The patient does make up the delayed dose(s) when the patient meets the protocol criteria to restart drugs.
- Discontinue = The specified drug(s) are totally stopped.

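### The pomalidomide table gives Grade 4 erythroderma no row of its own, and the catch-all row it falls to is looser or contradicts itself

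*Combined protocol and SAP*

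**What the plan says.** The adverse-event table in Section 8.41 (Pomalidomide Dose Modifications) has one erythroderma row, headed "Erythroderma \leq Grade 3". Its action is to omit pomalidomide and follow the patient weekly. It then adds: "If the AE resolves to \leq Grade 1 prior to Day 21, restart pomalidomide at next lower dose level".

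No other row names erythroderma. The last row of the table takes non-hematologic events not listed elsewhere, under "Other non-hematologic \geq Grade 3". That cell holds two instructions. It opens with "If the AE can be attributed to either of the drugs, pomalidomide should be discontinued at first instance b for recurrence" and runs on to speak of the same toxicity needing a dose change. It then says to omit the drug and continues: "If the toxicity resolves to \leq Grade 2 prior to Day 21, restart pomalidomide at next lower dose level".

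Other events in the table have Grade 4 assigned explicitly. An example is the row "Rash, maculo-papular Rash, acneiform Grade 4", whose action is permanent discontinuation of pomalidomide and removal from all study treatment.

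**The concern.** A dose-modification table should give each grade of a named event one action, and the action should not relax as the grade rises. Here the printed grade range stops at 3. Grade 4 is left to a general row that asks for less recovery before restart than the event's own row asks after Grade 3. The same general row also contains a damaged sentence about discontinuation, so two sites could treat the same Grade 4 event differently and both claim to follow the protocol.

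Patient safety is the main issue, but the trial data are also touched. Under Sections 4.1 and 13.1, patients who stop protocol treatment early are not followed further. Under Section 16.311, a patient counts towards the primary endpoint only after completing at least one cycle and supplying specimens before and after treatment. For an event in Cycle 1, the row that a site applies could therefore decide whether the patient enters the response-rate denominator.

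**Working it through.** No power or error rate is involved. The check sets the rows of the pomalidomide table side by side and asks which row takes each grade of erythroderma.

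| Event | Grades covered | Action | Recovery needed to restart |
|---|---|---|---|
| Erythroderma | 3 or lower | Omit, restart one level down | Grade 1 or lower |
| Maculopapular rash | 2 or 3 | Omit, restart one level down | Grade 1 or lower |
| Maculopapular or acneiform rash | 4 | Off all study treatment | No restart |
| Stevens-Johnson syndrome | 3-4 | Off all study treatment | No restart |
| Erythema multiforme | 3 or higher | Off all study treatment | No restart |
| Sensory neuropathy | 3 | Omit, restart one level down | Grade 1 or lower |
| Sensory neuropathy | 4 | Off all study treatment | No restart |
| Allergic reaction | 2-3 | Omit, restart one level down | Grade 1 or lower |
| Allergic reaction | 4 | Off all study treatment | No restart |
| Thromboembolic event | 3 or higher | Omit, anticoagulate, restart at same level | Investigator decides |
| Thyroid event | 2 or higher | Omit for rest of cycle, reduce one level | Not stated |
| Other non-hematologic | 3 or higher | Broken sentence on discontinuation, then omit and restart one level down | Grade 2 or lower |

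**Step 1: the sign as printed (Grade 3 or lower).**
- Grades 1 to 3 go to the erythroderma row, and the restart threshold is Grade 1 or lower.
- Grade 4 goes to the catch-all. If its restart text is followed, the threshold is Grade 2 or lower, one grade looser than after a Grade 3 event. If its opening sentence is read as discontinuation at first occurrence, there is no restart. The cell does not say which instruction governs.
- Grade 1 is inside the range that triggers omission and also inside the range that counts as recovered.

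**Step 2: comparison with neighbouring rows.** Five other skin, allergic or sensory-neuropathy rows reach Grade 4: Stevens-Johnson syndrome, erythema multiforme, Grade 4 rash, Grade 4 neuropathy and Grade 4 allergic reaction. All 5 of 5 remove the patient from study treatment. Rash, neuropathy and allergic reaction are each split by grade, and in each the action becomes stricter at Grade 4.

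**Step 3: the sign reversed (Grade 3 or higher).** The overlap at Grade 1 disappears, because Grades 1 and 2 would no longer trigger the row. The fall to the catch-all also disappears, because Grade 4 would sit in the erythroderma row with a Grade 1 threshold. What remains is a Grade 4 restart path where the five rows in Step 2 have removal.

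**Step 4: who could be affected.** Section 7.1 allows pomalidomide only in Cohorts C and D. Section 16.22 projects at most 63 patients in each, so the upper bound is 63 + 63 = 126 of 190 registered. The other 32 + 32 = 64, in Cohorts A and B, receive lenalidomide-based treatment and are outside this table. Cohort C and D patients may also be given lenalidomide, so the number on pomalidomide is 126 or fewer and is not stated.

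**The case against.** The case on the other side has several parts, and some of it stands.

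**The whole point may be one wrong character.** This is plausible. The Grade 1 overlap makes the printed sign look odd, and the text was read from PDF by a program. If the sign is wrong, the gap and the overlap are a single slip, not two faults. The row would still need checking, because the contrast in Step 3 survives.

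**The catch-all mentions discontinuation.** It does. A reader might infer that Grade 4 erythroderma is definitely allowed to restart at Grade 2. The documents do not support that as a settled reading, because the broken sentence can point the other way. The supportable statement is that the row is looser on one reading and conflicts with itself on the other.

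**Removal at Grade 4 is not a rule of the whole table.** This is correct. The thromboembolic and thyroid rows include Grade 4 and do not remove the patient. The lenalidomide catch-all in Section 8.1 also lets events of Grade 3 or higher resume after reaching Grade 2. The contrast is with the skin, allergic and sensory-neuropathy rows only.

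**Other guidance exists.** Section 8.0 refers adverse-event management to the prescribing information, and Section 13.2 lets the investigator stop treatment for an adverse event. Neither assigns Grade 4 erythroderma, and neither says whether it overrides the table.

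**The Grade 1 point can be pushed too far.** A reader might infer that a Grade 1 event leads at once to a lower dose. The row first requires omission and weekly follow-up. CTCAE 5.0 is also not reproduced, so the documents do not show how erythroderma is defined at each grade.

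**The Day 15 limit.** The allergic-reaction row uses "Grade 1 prior to Day 15, restart at next lower dose level and continue through Day 21", while the other rows with a day limit use Day 21. A reader might infer a further contradiction. Nothing in the documents requires different events to share a recovery limit, so this is no part of the point.

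**Conclusion.** The concern holds in a limited form. As printed, the table does not assign Grade 4 erythroderma, and the row that takes it is either less demanding than the rule for Grade 3 or internally conflicting. If the sign is reversed, the remaining issue is that erythroderma at Grade 4 is handled differently from the five comparable rows, without explanation.

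The conclusion rests on the sign being as read, on the catch-all being the row that receives an unassigned grade, and on erythroderma being gradable at 1 and 4 under the cited criteria. The 126 is a ceiling, and the number actually given pomalidomide is unknown. The documents give no rate for this event; that it is rare is an assumption. No measurable effect on the response rates is shown. The effect on the denominator is a possibility for Cycle 1 events only. The reason to act is that a safety rule should be readable in one way, and the repair is cheap.

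**What to change.** In Section 8.41 (Pomalidomide Dose Modifications):

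1. Check the inequality sign in the erythroderma row against the source document.
2. Reconcile that row's grade range with the other skin rows and with the catch-all, so that each grade to be acted on is assigned once and no grade is both trigger and recovered state.
3. Repair the opening sentence of the catch-all row, and make clear how it relates to the omit-and-restart text below it.
4. If Grade 4 erythroderma is meant to differ from the five removal rows, say so explicitly.

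The clinical team decides the actions themselves. The cost is wording in one table, to go into the next amendment, with no change to sample size, endpoints or analysis.

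### For other non-hematologic events of grade 3 or higher, one pomalidomide action cell says both to discontinue the drug and to omit and restart it, without saying when each applies

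*Combined protocol and SAP*

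**What the plan says.** The table stands under the heading "8.4 Pomalidomide–Related Treatment Modification Guidelines for Adverse Events". Its last row is labelled "Other non-hematologic adverse event" and covers grade 3 or higher, with pomalidomide as the agent. The action cell contains, in this order:

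- a condition: "If the AE can be attributed to either of the drugs";
- a first instruction under that condition: "pomalidomide should be discontinued at first instance b for recurrence of the same toxicity necessitating dose modification";
- a second instruction with no condition of its own: "Omit pomalidomide dose. Follow at least weekly";
- a continuation, if the toxicity resolves to grade 2 or better before Day 21: "restart pomalidomide at next lower dose level and continue through Day 21".

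The notes under the table define the action words: "Discontinue = The specified drug(s) are totally stopped" and "Omit = The current dose(s) for the specified drug(s) during a cycle is skipped". The definition of *Omit* adds that the skipped dose is not made up. It says nothing about resuming; in this row the resumption comes from the restart text.

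**The concern.** This is the residual row: it governs every severe non-hematologic event that no other pomalidomide row covers. A rule of that kind should lead any two investigators to the same action. Here one can read a permanent stop and another a temporary interruption with a lower dose afterwards, and each can point to the text.

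Safety management is at stake first. There may also be an analytic consequence. The primary endpoint is response after one cycle, and section 16.311 counts as evaluable only patients who complete at least one cycle and supply specimens before and after treatment. If the reading of this row changes whether a patient completes cycle 1, it could change who enters the response-rate denominator, for a reason linked to toxicity.

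**Working it through.** No alpha, power, effect size or event count enters this point, and the plan gives no figure to reproduce. The check compares texts.

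**1. Can both instructions apply to one event?** Under the table's own definition, a discontinued drug is totally stopped. The second instruction ends in a restart one level lower. A drug that has been totally stopped cannot be restarted, so for any one event at most one of the two can hold.

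**2. Does the attribution condition separate them?** It would if the cell said one thing for events that meet the condition and another for events that do not. It falls short in three ways:

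- The two drugs are not named. The listed cycle 1 pomalidomide regimen is pomalidomide with dexamethasone (section 7.1), so that pair is a reasonable guess, but the cell does not say so.
- The omit-and-restart text is not introduced as the alternative. It follows as a plain instruction.
- The table heading already confines the table to pomalidomide-related events. An event attributable to pomalidomide is attributable to one of the two drugs on an ordinary reading, so the condition would be met by nearly everything in the row.

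**3. Does another part of the protocol settle it?**

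- Section 8.0 sends dose modification to the prescribing information according to which drug is responsible. It is general and does not say which half of this cell prevails.
- The other rows of the pomalidomide table do not have the problem. Five rows stop the drug: Stevens-Johnson syndrome, erythema multiforme, grade 4 rash, grade 4 sensory neuropathy and grade 4 allergic reaction. None of them also gives a restart. Eight rows omit the dose: neutrophils, platelets, grade 2 or 3 rash, erythroderma, grade 3 sensory neuropathy, grade 2-3 allergic reaction, thromboembolism and thyroid disorder. None of them also discontinues. Of 5 + 8 + 1 = 14 rows, only this one does both.
- The matching lenalidomide row in section 8.1 gives a single path. It shows what one coherent instruction looks like, but it cannot be used to infer what was intended for pomalidomide.

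**4. What depends on the damaged words?** The stray letter between *first instance* and *recurrence* shows that something is lost or corrupted there, in the protocol or in the PDF text. With those words set aside, the cell still tells the investigator to discontinue at first instance and then to omit and restart. The conflict in step 1 remains.

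**5. Who is exposed?** Only Cohorts C and D list pomalidomide. Maximum accrual is 63 in each (section 16.22), so the ceiling is 63 + 63 = 126 patients, reached only if every patient received pomalidomide. The documents give neither the pomalidomide share nor the frequency of such events, so no expected count follows.

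**The case against.** The strongest reply is that the first instruction is conditional. On that view it is a special rule for events where either drug could be responsible, and omit-and-restart is the general rule. Section 8.0 does tie management to attribution, so the reading is available. It is not what the cell says, for the reasons in step 2, and an investigator would have to supply both the drug names and the missing alternative.

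A second reply is that the garbled words may be an extraction fault and may once have separated first occurrence from recurrence. That is fair. The run from first instance to recurrence should not be held against the plan.

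A reader might also infer something stronger: that a stop under this row takes the patient off study and out of the primary denominator. The documents do not support that as a certainty:

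- The five stopping rows also take the patient off all study treatment. This row has no such wording.
- The definition of *Discontinue* reaches only the drug specified. The schema and section 13 speak of discontinuing treatment, not of stopping one agent. Some lenalidomide rows in section 8.1 expressly let a patient go on with the remaining agents.
- Section 16.311 does not define completing a cycle and does not say that stopping one agent makes a patient non-evaluable.
- Cycle 1 lasts 21 days. An omitted dose that has not resolved before Day 21 also leaves the rest of cycle 1 without pomalidomide, so the two readings may not differ in evaluability for that patient.

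The effect remains possible. Cycles 2-6 in Cohorts C and D must contain lenalidomide or pomalidomide, so a patient who stops pomalidomide has no listed regimen unless switched, and the row does not address switching.

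**Conclusion.** The point holds as an internal inconsistency in one cell. As written, the row gives two mutually exclusive actions and no usable rule for choosing between them. The conclusion rests on the legible words of the cell and on the table's own definition of *Discontinue*. It assumes only that the garbled stretch did not contain the missing rule, which the PDF text cannot show either way.

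The consequence that follows directly is inconsistent management of the same event. An effect on evaluability in Cohorts C and D is possible but conditional on how completing a cycle is applied. It should not be reported as an established bias in the response rate. The size cannot be given beyond the ceiling of 126 patients. The correction should be made because the row concerns severe toxicity and the change is cheap.

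**What to change.** The sponsor should first check the cell against the source protocol file, to see whether words were lost. It should then reconcile the instructions so that the cell:

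- states, in the table's defined terms, when each action applies, including first occurrence as against recurrence;
- names the drugs meant in the attribution condition and says what applies when the condition is not met;
- says whether stopping pomalidomide under this row ends study treatment, as the other stopping rows do.

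It would help to add a sentence to section 16.311 on whether a patient whose pomalidomide is stopped or interrupted in cycle 1 counts as having completed the cycle. Which action is intended is for the sponsor to decide; this review proposes none.

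The cost is a clarification amendment, with no change to sample size or analysis method. If patients have already been managed under this row, the action taken for each should be listed so that any difference in practice is visible.
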